2. OBJECTIVES AND ENDPOINTS

Objectives	Endpoints
Primary	
To compare incisal bite force for test	AOB at 12 hours.
adhesive 1 versus no adhesive after 12	
hours.	
To compare incisal bite force for test	AOB at 12 hours.
adhesive 2 versus no adhesive after 12	
hours.	
Secondary	
To compare incisal bite force for test	AOB at 12 hours.
adhesive 1 versus Super Poligrip® Free	
after 12 hours.	
To compare incisal bite force for test	AOB at 12 hours.
adhesive 2 versus Super Poligrip [®] Free	
after 12 hours.	
To compare incisal bite force between	AOB at 12 hours.
test adhesives 1 & 2 after 12 hours.	
Other	
To compare incisal bite force for test	AOB at 0.5, 1, 3, 6 and 9 hours.
adhesive 1 versus no adhesive over 9	
hours.	
To compare incisal bite force for test	AOB at 0.5, 1, 3, 6 and 9 hours.
adhesive 2 versus no adhesive over 9	
hours.	
To compare incisal bite force for test	AOB at 0.5, 1, 3, 6 and 9 hours.
adhesive 1 versus Super Poligrip [®] Free	
over 9 hours.	
To compare incisal bite force for test	AOB at 0.5, 1, 3, 6 and 9 hours
adhesive 2 versus Super Poligrip® Free	
over 9 hours.	
To assess subjects' preference with	Scores from subject-completed
regards to denture adhesive ooze, flavor/	questionnaires on product ooze, at 0.5
after-taste, texture and assess ease of	hours, and flavour/ after-taste, texture and
removal	ease of removal after 12 hours' use
To assess the ease of extrusion of the	Scores from subject-completed
product from the tube by the subjects	questionnaire on product extrusion after
post bite force phase	12 hours' use

Document Name	Project CO protocol		
Туре	Version	Document Identifier	Effective Date
eldo clinical doc	5.0; Most-Recent; Effective; CURRENT	090032d580cfe581	23-Feb-2017 14:35:47
Reason For Issue	Auto Issue		

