9.2.4. Handling of Dropouts and Missing Data

For calculation of AOB, linear interpolation will be used in the case of missing values. If more than one of the assessments during the 12 hour period is missing, AOB will be set to missing.

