PP	Per Protocol
PT	Preferred Term
SAE	Serious Adverse Event
SAP	Statistical Analysis Plan
SD	Standard Deviation
SOC	System Organ Class

Document Name	Statistical Analysis Plan for Study 206233.docx		
Туре	Version	Document Identifier	Effective Date
eldo clinical doc	1.0; CURRENT; Most-Recent; Effective	090032d580d17d34	27-Mar-2017 09:54:18
Reason For Issue	Auto Issue		

1 Introduction

This document describes the statistical methods and data presentations to be used in the summary and analysis of the final data from Protocol 206233. This Statistical Analysis Plan (SAP) will be approved before unblinding and database freeze.

SAS version 9.4 will be used for the analyses. All statistical analyses mentioned in this SAP will be performed by inVentiv Health Clinical.

2 Objectives

Objectives	Endpoints
Primary	_
To compare incisal bite force for test adhesive 1 versus no adhesive after 12 hours.	AOB at 12 hours.
To compare incisal bite force for test adhesive 2 versus no adhesive after 12 hours.	AOB at 12 hours.
Secondary	
To compare incisal bite force for test adhesive 1 versus Super Poligrip® Free after 12 hours.	AOB at 12 hours.
To compare incisal bite force for test adhesive 2 versus Super Poligrip® Free after 12 hours.	AOB at 12 hours.
To compare incisal bite force between test adhesives 1 & 2 after 12 hours.	AOB at 12 hours.
Other	
To compare incisal bite force for test adhesive 1 versus no adhesive over 9 hours.	AOB at 0.5, 1, 3, 6 and 9 hours.
To compare incisal bite force for test adhesive 2 versus no adhesive over 9 hours.	AOB at 0.5, 1, 3, 6 and 9 hours.
To compare incisal bite force for test adhesive 1 versus Super Poligrip® Free over 9 hours.	AOB at 0.5, 1, 3, 6 and 9 hours.
To compare incisal bite force for test adhesive 2 versus Super Poligrip® Free over 9 hours.	AOB at 0.5, 1, 3, 6 and 9 hours
To assess subjects' preference with regards to denture adhesive ooze, flavor/	Scores from subject-completed questionnaires on product ooze, at 0.5

Document Name	Statistical Analysis Plan for Study 206233.docx		
Туре	Version	Document Identifier	Effective Date
eldo clinical doc	1.0; CURRENT; Most-Recent; Effective	090032d580d17d34	27-Mar-2017 09:54:18
Reason For Issue	Auto Issue		

after-taste, texture and assess ease of	hours, and flavour/ after-taste, texture and
removal	ease of removal after 12 hours' use
To assess the ease of extrusion of the	Scores from subject-completed
product from the tube by the subjects	questionnaire on product extrusion after

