8.1 Primary Efficacy Analysis

Incisal Bite Force (lbs): Area over Baseline (AOB₀₋₁₂)

The Area Over Baseline (AOB) over 12 hours for the incisal bite force (lbs) (denoted by AOB_{0-12}) is the primary efficacy variable.

To calculate this variable first the Area Under the Curve (AUC) is calculated from 0 to 12 hours (AUC₀₋₁₂) using the trapezoidal method. AOB₀₋₁₂ will be calculated as (AUC₀₋₁₂)/12 minus baseline bite force (lbs). This transformation will return the measurement to the same scale as the original observations whilst also looking at the average amount of improved force over time by subtracting the baseline value (AOB: Area Over Baseline). Higher values of AOB demonstrate a stronger bite force over time than lower values.

Document Name	Statistical Analysis Plan for Study 206233.docx		
Туре	Version	Document Identifier	Effective Date
eldo clinical doc	1.0; CURRENT; Most-Recent; Effective	090032d580d17d34	27-Mar-2017 09:54:18
Reason For Issue	Auto Issue		

Missing readings will be ignored and interpolation will be made between pre and post the missing values, if necessary. In the case of more than one missing value or if the 12 hour value or the baseline value is missing, the AOB will be set to missing.

An analysis of covariance (ANCOVA) model will be used with AOB values as the response, with fixed effect factors for treatment group, period and subject-level baseline, period level baseline minus subject-level baseline as covariates. Subject will be included as a random effect.

From the above model, treatment differences between groups, (each of the two adhesives versus no adhesive), 95% confidence intervals and p-values, will be provided. The confidence intervals and p-values will be adjusted using the Dunnett's method so that the overall confidence level for the two confidence intervals is maintained at 95% and the two treatment comparisons can be performed with an overall 5% significance level.

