8.3 Exploratory/Other Efficacy Analysis

Incisal Bite Force (lbs): Area over Baseline ($AOB_{0-0.5}$, AOB_{0-1} , AOB_{0-3} , AOB_{0-6} , AOB_{0-9})

Other efficacy bite-force efficacy variables analysed will be bite force AOBs over 0.5, 1, 3, 6 and 9 hours respectively. Each of these variables will be analysed using a similar ANCOVA model as described above for the primary efficacy variable.

From this model, treatment difference between each test adhesive versus Super Poligrip® Free, the treatment difference between each test adhesive versus no adhesive, 95% confidence intervals and p-values, will be provided. All significance tests will be conducted at the two sided 5% significance level.

Document Name	Statistical Analysis Plan for Study 206233.docx		
Туре	Version	Document Identifier	Effective Date
eldo clinical doc	1.0; CURRENT; Most-Recent; Effective	090032d580d17d34	27-Mar-2017 09:54:18
Reason For Issue	Auto Issue		

The data from the questionnaires and the denture adhesive weights will be listed and tabulated using descriptive statistics.

9 Safety Analysis

The safety profile of the study treatments will be assessed with respect to adverse events (AEs) and incidents. Oral soft tissue (OST) abnormalities are included as AEs if they appear or worsen after the initial assessment.

All safety data will be reported for the Safety population as per actual treatment received. All subjects screened will be included in the list of AEs.

All AEs will be reviewed by the Clinical Research Director or Designee prior to database freeze and will be coded using the Medical Dictionary for Regulatory Activities (MedDRA). During this review stage, AEs will be further categorized as oral or non-oral.

AEs will be regarded as treatment emergent if they occur on or after the date and time of the pre-treatment OST exam at the randomisation visit. All other AEs prior to this will be considered non-treatment emergent. AEs that occur during inter-test day washout are assigned to the last treatment received.

The following summary tables and listings will be presented by treatment group.

- Table of treatment emergent AEs by Oral/Non-Oral and Preferred Term
- Table of treatment emergent AEs by SOC and Preferred Term
- Table of Treatment emergent treatment related AEs by Oral/Non-Oral and Preferred Term
- Listing of all AEs (including Non-treatment emergent from All Subjects).

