- Listing of serious AEs. (if there are none a null listing will be produced, if there are >5 treatment emergent SAEs a table will be produced by SOC and PT)
- Table of Non Serious treatment emergent AEs by SOC and Preferred Term.
 (only produced if there are > 5 SAEs)
- Listing of incidents (if there are none a null listing will be produced)

Document Name	Statistical Analysis Plan for Study 206233.docx		
Туре	Version	Document Identifier	Effective Date
eldo clinical doc	1.0; CURRENT; Most-Recent; Effective	090032d580d17d34	27-Mar-2017 09:54:18
Reason For Issue	Auto Issue		

No inferential analyses will be performed to compare treatments with respect to safety.

10 Interim Analysis

No interim analysis is planned for this study.

11 Topline Summary

The following outputs will be produced for the topline report.

Datasets/Tables	Description
Datasets	STAT1, STAT2
Tables	Table 9.1.1 – Subject Disposition
	Table 9.1.3 – Protocol Violations Leading To Exclusion From Per Protocol Analysis – ITT Population
	Table 9.3.1 – Summary of Bite Force (lbs) by Time – ITT Population
	Table 9.3.2.1 – Summary of AOB by Time – ITT Population
	Table 9.3.2.2 – Summary of AOB (0-12 Hours) – PP Population
	Table 9.4.4 – Listing Of All Adverse Events – All Subjects

The following table will be produced in .rtf format for input into the topline report:

Document Name	Statistical Analysis Plan for Study 206233.docx		
Туре	Version	Document Identifier	Effective Date
eldo clinical doc	1.0; CURRENT; Most-Recent; Effective	090032d580d17d34	27-Mar-2017 09:54:18
Reason For Issue	Auto Issue		

Table 1: Statistical Analysis of Between Treatment Group AOB over 12 hours (ITT Population)

Parameter	Time Point	Treatment Comparison	Difference	Lower CI	Upper CI	P-value
AOB	0-12 hours	Super Poligrip Free vs. No Adhesive	X.XX	X.XX	x.xx	x.xxxx
		Test Adhesive 1 vs. No Adhesive	X.XX	X.XX	X.XX	x.xxxx
		Test Adhesive 2 vs. No Adhesive	X.XX	X.XX	x.xx	x.xxxx
		Test Adhesive 1 vs. Super Poligrip Free	X.XX	x.xx	x.xx	x.xxxx
		Test Adhesive 2 vs. Super Poligrip Free	X.XX	X.XX	X.XX	x.xxxx
		Test Adhesive 1 vs. Test Adhesive 2	x.xx	X.XX	X.XX	x.xxxx

Positive control adhesive: Super Poligrip Free Adhesive Cream (USA); Test Adhesive 1: CC Test Adhesive 2: CC No adhesive [1] From ANCOVA with period and treatment as fixed effects, subject as random effect, and subject-level and period-level pre treatment baseline

bite force (parameterized as period-level minus subject-level) as covariates.

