Table 9.3.4	Summary of Questionnaire Data – All Randomised Subjects		Appendix 3
Table 9.4.1	Treatment Emergent Adverse Events by Oral/Non-Oral and Preferred Term – Safety Population	X	
Table 9.4.2	Treatment Emergent Adverse Events by System Organ Class (SOC) and Preferred Term – Safety Population	X	
Table 9.4.3	Treatment Related Treatment Emergent Adverse Events by Oral/Non-Oral and Preferred Term – Safety Population	X	
Table 9.4.4	Listing of All Adverse Events – All Subjects	X	
Table 9.4.5	Listing of Serious Adverse Events – All Subjects	X	
Table 9.4.6 [#]	Non-Serious Treatment Emergent Adverse Events by System Organ Class (SOC) and Preferred Term – Safety Population ed if there are >5 SAEs		9.4.2

Only produced if there are >5 SAEs.

Document Name	Statistical Analysis Plan for Study 206233.docx		
Туре	Version	Document Identifier	Effective Date
eldo clinical doc	1.0; CURRENT; Most-Recent; Effective	090032d580d17d34	27-Mar-2017 09:54:18
Reason For Issue	Auto Issue		

FIGURES

Figure No.	Figure Title (including population)	Standard	Template
Figure 9.1	Subject Profiles of Bite Force (lbs) – Intent To Treat Population		Appendix 3
Figure 9.2	Bite force (lbs) value over time by treatment – Intent To Treat Population		Appendix 3

LISTINGS

Listing No.	Listing Title	Standard	Template
Listing 2.1	Randomisation Information – All Randomised Subjects	X	
Listing 2.2	Denture Removal Questionnaire, Question 3 (Please describe below what you liked or dislike about the denture adhesive) – All Randomised Subjects		Appendix 3
Listing 2.3	Incidents – All Subjects	X	

Document Name	Statistical Analysis Plan for Study 206233.docx		
Туре	Version	Document Identifier	Effective Date
eldo clinical doc	1.0° CURRENT: Most-Recent: Effective	090032d580d17d34	27-Mar-2017 09:54:18
Reason For Issue	Auto Issue		

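### Do the objectives worded 'after 12 hours' require a separate modelled comparison of bite force at the 12 h reading?

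*SAP*

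**What the plan says.** Protocol section 2 (and the synopsis) and SAP section 2 word both primary and all three secondary objectives as comparisons after 12 hours. The first in the SAP is "To compare incisal bite force for test adhesive 1 versus no adhesive after 12 hours"; the protocol has "adhesive 1 versus no adhesive after 12" hours. In each row the paired endpoint is AOB at 12 hours. The neighbouring 'other' bite-force objectives say over 9 hours, and their endpoint is AOB at 0.5, 1, 3, 6 and 9 hours.

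SAP 8.1 defines the primary variable as AUC0-12 by the trapezoidal method, divided by 12, minus baseline. It describes the purpose as returning to the original scale "whilst also looking at the average amount of improved force over time by subtracting the baseline value". It also says that "if the 12 hour value or the baseline value is missing, the AOB will be set to missing".

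SAP 8.3 adds AOB over 0.5, 1, 3, 6 and 9 hours: "Each of these variables will be analysed using a similar ANCOVA model as described above for the primary efficacy variable". Table 9.3.3.1 reports these with differences, 95% CIs and p-values. SAP section 11 carries AOB0-12 alone into the topline: "Table 1: Statistical Analysis of Between Treatment Group AOB over 12 hours (ITT Population").

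Bite force at single times appears in Table 9.3.1 (N, mean, SD, SE, median and range per treatment, repeated up to 12 hours), in Figure 9.1, "Subject Profiles of Bite Force (lbs"), and in Figure 9.2, bite force over time by treatment.

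**The concern.** Read literally, a comparison after 12 hours asks whether the adhesive still holds at the end of the day. An average over the day can be high because of the early and middle hours while hold has gone by hour 12. The 'other' objectives say over 9 hours, so the contrast with after 12 hours could be taken as deliberate.

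If so, a significant AOB0-12 would be reported as meeting an objective that it does not address. The readings that do address it would have no within-subject interval. The per-arm standard errors in Table 9.3.1 are no substitute. They contain the between-subject variation that protocol 3.4 calls high and gives as the reason for a crossover. What would be at stake is the reading of a proof-of-principle result used to choose formulations for further work.

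**Working it through.** **Inputs.** Reading times 0.5, 1, 3, 6, 9 and 12 h (protocol 3.1). Planning difference 2.01 lb, residual SD 1.929 lb and 18 completers (protocol 9.1, SAP 4). Assumed: the pre-treatment baseline is the time-0 value, and 1.929 lb is the residual SD of AOB0-12. The documents state neither outright.

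**The plan's own figure.** SE of a difference = 1.929 × √(2/18) = 0.643 lb. With a Dunnett critical value of about 2.28 (47 to 48 df), simulation gives power of 80.9% when the other product is 1 lb better than no adhesive and 80.6% when it is no better. The stated figure of about 81% is reproduced, and nothing below affects it.

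**Weights in AOB0-12.** Each reading's weight is half the sum of its adjacent intervals, divided by 12:

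| Hour | 0 | 0.5 | 1 | 3 | 6 | 9 | 12 |
|---|---|---|---|---|---|---|---|
| Weight | 2.1% | 4.2% | 10.4% | 20.8% | 25% | 25% | 12.5% |

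The 12 h reading has 1.5/12 = 12.5%. The arithmetic behind the concern is right.

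**Would the planned outputs hide a late loss?** Take two invented treatment-effect profiles, each with an AOB0-12 difference of 2.01 lb:

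- Sustained: a constant 2.01/0.9792 = 2.05 lb from 0.5 to 12 h.
- Lost at 12 h: 2.01/0.8542 = 2.35 lb from 0.5 to 9 h, then zero.

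| Planned output | Sustained | Lost at 12 h |
|---|---|---|
| AOB0-12 difference (Table 9.3.3.1) | 2.01 | 2.01 |
| AOB0-9 difference (Table 9.3.3.1) | 2.00 | 2.29 |
| 12 h mean minus no-adhesive 12 h mean (Table 9.3.1) | 2.05 | 0.00 |

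The last row separates the profiles plainly. When every subject completes every period, the difference of two arm means equals the mean within-subject difference, before adjustment for period and baseline. It can be read off directly.

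The AOB0-9 to AOB0-12 comparison is also sharper than it looks. Each estimate has a 95% half-width of about 1.3 lb (for AOB0-12, 2.012 × 0.643 = 1.29), but they share most of their readings. With an assumed common correlation ρ of 0.3 to 0.8 among post-baseline changes, the two estimates correlate 0.97 to 0.996. The half-width of the fall itself is 0.12, 0.23 and 0.31 lb at ρ = 0.8, 0.5 and 0.3, and 0.44 lb at ρ = 0.1. The illustrated fall is 0.28 lb. The plan does not report this interval, but 1.3 lb is the wrong yardstick for the fall.

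**What would a 12 h interval add?** The documents give no SD for a single reading. Under the same equal-correlation assumption, SD at 12 h = 1.929/√(ρ × 0.9792² + (1 − ρ) × 0.1966), where 0.9792 is the sum and 0.1966 the sum of squares of the post-baseline weights. Half-width = 2.012 × SD × √(2/18), on 47 df:

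| ρ (assumed) | 12 h SD (lb) | Half-width (lb) | Unadjusted power for 2.01 lb |
|---|---|---|---|
| 0.8 | 2.15 | 1.44 | 79% |
| 0.5 | 2.54 | 1.70 | 64% |
| 0.3 | 2.96 | 1.98 | 51% |
| 0.2 | 3.27 | 2.19 | 44% |
| 0.1 | 3.69 | 2.48 | 36% |

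**The case for a change.** The best case for a change is this. No listed table, figure or topline output is described as giving a within-subject treatment difference at 12 h with an interval. Protocol 9.2.3.1 says that observed mean differences will be weighed as well as significance, so persistence of hold could bear on the decision. The data exist, and the missing-data rule means that every subject-period in the primary analysis already has both a baseline and a 12 h reading. One more run of the same model, labelled descriptive, would cost almost nothing. Table 9.3.1 cannot replace it: an interval built from per-arm SEs would be √(1 + ratio) times too wide, that is 1.4 to 2.0 times if between-subject variance is assumed to be 1 to 3 times within-subject variance.

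Most of those facts stand. The interval is absent, and the per-arm SEs do not supply it. The inference that the plan needs it does not stand. It rests on one phrase read apart from its endpoint cell. The plan's usage of AOB at a time is visible in the neighbouring rows: AOB at 0.5 to 9 hours is analysed in SAP 8.3 as AOB over those hours. The protocol's brief summary speaks of a 12 hour period, and protocol 9.2.3.1, protocol 9.3.2 and SAP 8.1 all define the primary variable over 12 hours. Once after is understood as over, no stated objective calls for a 12 h point contrast. What is left is an optional extra analysis, for which the study was not sized and which could be over-read beside the primary result.

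**Conclusion.** No change is called for. The wording is a clerical slip: five objectives say after where their endpoint and every operative definition mean over 0 to 12 hours. An analyst following the SAP would compute the intended variable, and the conclusion about average hold over 12 hours would be sound. The Dunnett adjustment, success rule and sample size are unaffected.

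The substantive remainder is small. A late loss of hold would show as a point estimate in Table 9.3.1, 2.05 against 0.00 lb in the example, and the fall from AOB0-9 to AOB0-12 would point the same way. Only the precision of the 12 h difference is unreported. That precision would be modest, with a half-width of 1.44 to 2.48 lb for assumed correlations of 0.8 to 0.1. A team wanting the interval could obtain it afterwards from data already collected, as a descriptive supplement.

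The figures rest on the baseline as time-0 value (weight 2.1%), complete data from 18 subjects, equal correlation between readings, and invented profiles. The reading of the objectives depends on none of these.

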3.1. Study Product

The following study products will be supplied by the Clinical Supplies Department, GSKCH:

	Test Product 1	Test Product 2	Reference Product	Negative Control
Product	Test adhesive 1	Test adhesive 2	Super	No adhesive
Name	with a thin	with a thin	Poligrip® Free	_,
	nozzle	nozzle	Adhesive	
			Cream (USA	
			marketplace)	
Product	CCI	CCI	CCI	N/A
Formulation				
Code (MFC)				
Dose	Continuous	Continuous	3 dabs for	N/A
	strips applied	strips applied	upper denture	
	to upper	to upper	as per the	
	denture as per	denture as per	product label	
	the application	the application	application	
	instructions	instructions	instructions	
Route of	Oral topical	Oral topical	Oral topical	N/A
Administrat				
ion				
Dosing	applied to clean	applied to clean	applied to clean	N/A
Instructions	dry denture fit	dry denture fit	dry denture fit	
	surface in a	surface in a	surface in a	
	pattern	pattern	pattern	
	consistent with	consistent with	consistent with	
	the application	the application	the product	
	instructions	instructions	label	
			application	
			instructions	

Document Name	Statistical Analysis Plan for Study 206233.docx		
Туре	Version	Document Identifier	Effective Date
eldo clinical doc	1.0; CURRENT; Most-Recent; Effective	090032d580d17d34	27-Mar-2017 09:54:18
Reason For Issue	Auto Issue		

4 Sample Size Determination

Approximately 25 subjects will be screened to randomize approximately 21 subjects to ensure that approximately 18 evaluable subjects complete the study.

A sample size of approximately 18 subjects completing all treatment periods will provide approximately 81% power to detect a difference of 2.01 lbs in at least one of the two test products from no adhesive, using two-sided t-tests with family wise significance level of 5% based on the Dunnett's adjustment, assuming a residual standard deviation of 1.929 lbs. The estimate of SD is obtained from the study. This was the larger SD among two similar earlier studies:

The delta of 2.01 was obtained from the study. In that study this was the observed difference between Super Poligrip and no adhesive. This was the lowest observed delta for Super Poligrip vs no adhesive among the studies.

As such the expected performance of the test products is completely unknown but we would like at least one test product to perform like Super Poligrip or better.

Power calculations were performed for 2 alternative hypotheses:

- 1. One of the treatment means is 2.01 lbs more than the mean for no adhesive; the other treatment mean is 1 lb more than the mean for no adhesive
- 2. One treatment mean is 2.01 lbs more than the mean for no adhesive; the other treatment mean is the same as the mean for no adhesive

The power was approximately 81% for both the cases.

The results are based on 100,000 simulations.

5 Data Considerations

